9.1.1 Dose Adjustments

Analysis of available PK data from studies 111-101 and 111-202 indicated that differences in subject body weight did not directly translate to differences in total body clearance of BMN 111. The same weight-based dose in the pediatric population of Study 111-202 (5-12 years old) yielded lower exposure (C_{max} and AUC) than that characterized in the adult population of Study 111-101. Therefore, the same weight-based dose in the young pediatric population in this study may yield exposure less than the target exposure range characterized to be safe and effective in Study 111-202 at the 15 μ g/kg dose. Since this is the first experience with BMN 111 in this young pediatric population, it is also possible the exposure at 15 μ g/kg could be greater than the target exposure range, and dose adjustment may be warranted. Thus, an option for adjustment of the weight-based dose is provided to ensure that the appropriate target exposure for safety and efficacy is reached for the young subjects in this study.

The need for dose adjustment will be evaluated as follows: three sentinel subjects in Cohort 1 will receive an initial dose of 15 μ g/kg. After all three sentinel subjects reach Day 8, the Sponsor will review and evaluate all available safety and PK data (at minimum). If the criteria for dose adjustment are met, the three sentinel subjects will be started on the new adjusted dose at their next scheduled visit, and vital signs will be obtained for at least 4 hours post-dose.

The remainder of the subjects in the age cohort will also be enrolled starting at the new adjusted dose. After the third sentinel subject reaches Week 12 post dose adjustment, a DMC review will occur to evaluate all safety and PK data and, upon endorsement, the three sentinel subjects from the next younger cohort will be enrolled starting at the new adjusted dose. The three sentinel subjects for the second and third cohorts will be evaluated similarly to the sentinel subjects in the first cohort for potential dose adjustment.

As subjects age on study, they will be administered the dose determined to be appropriate for their current age. For example, if a subject enrolls into Cohort 2 at age 20 months, they will receive the recommended dose for subjects aged ≥ 6 to < 24 months until they turn 24 months in age. When they turn 24 months in age, they will begin to receive the recommended dose for subjects aged ≥ 24 to < 60 months.

Criteria for Dose Adjustment

The criteria for dose adjustment are based on obtaining equivalent exposure characterized to be safe and effective with the 15 μ g/kg dose in Study 111-202 in each of the age cohorts evaluated in this study. BMN 111 dose may be adjusted if the mean observed AUC_{0-120} from

sentinel subjects is less than the 25th percentile for AUC₀₋₁₂₀ in Cohort 3 (15 µg/kg) of Study 111-202 or greater than the 75th percentile in Cohort 3 of Study 111-202. If these criteria are met, an allometric scaling coefficient, α , for BMN 111 clearance by subject body weight will be determined using a population PK modelling approach and available data from this study and Studies 111-202 and 111-101. The recommended adjusted dose will be determined using the following expression:

$$Dose_{ch} = Dose_{ref} \left(\frac{WT_{ch}}{WT_{ref}} \right)^\alpha$$

where WT_{ref} and $Dose_{ref}$ are the typical (i.e., median) subject body weight and total dose, respectively, at the 15 µg/kg dose level in Cohort 3 of Study 111-202, and WT_{ch} is the anticipated median weight in the age cohort being studied. As such, the recommended adjusted dose will target the median AUC₀₋₁₂₀ observed at the 15 µg/kg dose level of Study 111-202. The recommended adjusted dose, $Dose_{ch}$, will be normalized by WT_{ch} , to provide the recommended adjusted weight-based dose. The following rules will be used for dose adjustment:

- A maximum of a 2-fold increase in dose/kg will be permitted between dose adjustments regardless of exposure.
- The total dose will not exceed the highest total dose administered in Study 111-202.

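### Section 9.1.1 sends both exposure triggers to one dose expression, so it can recommend a higher dose per kg after sentinel exposure is found above target

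*Protocol*

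**What the plan says.** Section 9.1.1 (Criteria for Dose Adjustment) sets two opposite triggers on the mean AUC0-120 of the three sentinels: below the 25th percentile of Study 111-202 Cohort 3 (15 µg/kg), or "greater than the 75th percentile in Cohort 3 of Study 111-202". If the criteria are met, an allometric exponent α for clearance on body weight is estimated by population PK from this study and Studies 111-202 and 111-101. Then: "The recommended adjusted dose will be determined using the following expression". The expression is Dose_ch = Dose_ref × (WT_ch/WT_ref)^α. WT_ref and Dose_ref are the median weight and total dose at 15 µg/kg in Study 111-202, and WT_ch is the anticipated median weight of the age cohort. The section continues: "As such, the recommended adjusted dose will target the median" AUC0-120 of that reference group.

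Two rules follow. One reads "A maximum of a 2-fold increase in dose/kg will be permitted between dose adjustments regardless of exposure". The other caps the total dose at the highest total dose given in Study 111-202.

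On the earlier data, section 9.1.1 says that "differences in subject body weight did not directly translate to differences in total body clearance of BMN 111", and that the children of Study 111-202 had lower exposure at the same weight-based dose "than that characterized in the adult population of Study 111-101". It also accepts that exposure here could exceed the target range: "Since this is the first experience with BMN 111 in this young pediatric population".

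The adjusted dose goes to the sentinels at their next scheduled visit. In addition, "The remainder of the subjects in the age cohort will also be enrolled starting at the new adjusted dose".

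**The concern.** The trigger is two-sided but the response is not. Exposure that is too low and exposure that is too high lead to the same formula, which contains weights and α but not the observed sentinel AUC; that enters only by way of the pooled α. If the pooled α stays below 1, the formula returns more than 15 µg/kg even when the high trigger was the reason for using it.

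At stake is the direction of a dose change in infants and young children, in a trial whose protocol names hypotension as a potential risk. The step from trigger to adjusted dose within the cohort rests on the Sponsor's Day 8 review. This is a rule fixed in the protocol, not a detail left for the SAP.

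**Working it through.** **Inputs.** From section 9.1.1: the expression, the 15 µg/kg reference dose, the two triggers and the two rules. The protocol gives no value for α, WT_ch or WT_ref, so the weights below are assumptions for Cohort 1: WT_ch/WT_ref from 12/25 kg (0.48) to 15/20 kg (0.75), with 13/22 kg (0.59) in the middle. That WT_ch is below WT_ref follows from the ages: under 60 months here, 5 years or more in Study 111-202.

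**Step 1: sign of the change.** Since Dose_ref/WT_ref = 15 µg/kg,

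Dose_ch/WT_ch = 15 × (WT_ch/WT_ref)^(α−1).

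With WT_ch/WT_ref < 1, this exceeds 15 exactly when α < 1.

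| α | 15/20 kg | 13/22 kg | 12/25 kg |
|---|---|---|---|
| 0.5 | 17.3 | 19.5 | 21.7 |
| 0.75 | 16.1 | 17.1 | 18.0 |
| 0.9 | 15.4 | 15.8 | 16.1 |
| 1.0 | 15.0 | 15.0 | 15.0 |
| 1.1 | 14.6 | 14.2 | 13.9 |

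This threshold applies to a start from 15 µg/kg. A later cohort may start from an already adjusted dose, and the α at which its dose would rise then differs.

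**Step 2: which side of 1 the earlier data suggest.** At a common µg/kg dose, AUC is proportional to W/CL = W^(1−α). Lower AUC in lighter children than in adults corresponds to α < 1 if weight is the only explanation. The adults of Study 111-101 were healthy men without achondroplasia, so it may not be.

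**Step 3: whether the rules prevent an increase.**
- Two-fold cap: it binds only if (WT_ch/WT_ref)^(α−1) > 2. At 0.48 this needs α < 1 − ln 2/ln(25/12) = 1 − 0.693/0.734 ≈ 0.06. It does not bind at any α in the table.
- Total-dose cap: for any α > 0, Dose_ch is below Dose_ref, and Dose_ref was itself given in Study 111-202. At the cohort's median weight the cap cannot bind.

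Neither rule ties the direction of change to the trigger.

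**Step 4: what a wrong-direction change would do.** Assume a log-SD of 0.4 for the reference AUC. The 75th percentile is then exp(0.6745 × 0.4) = 1.31 times the median. At 13/22 kg and α = 0.75 the dose ratio is 17.1/15 = 1.14. If AUC is proportional to dose, sentinel AUC moves from 1.31 to 1.31 × 1.14 = 1.49 times the reference median. Reaching the median would take 15/1.31 = 11.5 µg/kg, which the expression returns only if α = 1 + 0.270/0.526 ≈ 1.51. The targeting statement therefore holds only if the sentinels' clearance lies on the fitted curve.

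**Step 5: effect of refitting α with the sentinels.** Over-exposed sentinels pull α upward. Two stand-ins for the unspecified model, each with three sentinels at 1.3 to 2 times the reference median, bracket the result:
- *Weight as the only covariate, adults included* (20 or 30 adults at 75 kg; 20 or 35 reference children at 20, 22 or 25 kg; sentinels at 12, 13 or 15 kg). The output is 16.8–20.2 µg/kg if α in the earlier data is 0.5, 15.7–17.2 at 0.75, 14.3–15.6 at 0.9 and 13.4–14.9 at 1.0.
- *Adult difference absorbed by the model*, approximated by leaving the adults out (children at 22 kg, log-weight SD 0.2, log-clearance SD 0.35; sentinels at 13 kg; earlier α 0.5 to 0.9). The median output is about 9.8–13.8 µg/kg with 10 reference children, 11.0–15.0 with 20 and 12.1–16.0 with 35.

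Both increases and reductions are reachable. The protocol does not support choosing one model over the other.

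**The case against.** The strongest reply has four parts.

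1. *Adjustment is optional and aims at a stated exposure.* Section 9.1.1 says the dose may be adjusted, calls the output a recommendation and bases the criteria on matching Study 111-202 exposure. A Sponsor who saw over-exposure would hardly raise the dose. This lowers the likelihood. It does not change the rule as written, which names one expression and contains no directional limit.

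2. *A high trigger with α truly below 1 should be uncommon, and often chance.* If the power curve holds in these children, lighter subjects are expected to be under-exposed at 15 µg/kg. With three sentinels at 13/22 kg and log-SD 0.35, the chance that their mean exceeds the 75th percentile is roughly 1% at α = 0.5, 5% at 0.75 and 11% at 0.9 (0.3% to 14% over weight ratios 0.48 to 0.75). In such a case a modest increase would be right for the cohort. This stands. The hazard is the other case, where clearance in the young lies below the fitted curve.

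3. *Safeguards exist.* Section 9.1.1 requires DMC review and endorsement, after the third sentinel reaches Week 12 post-adjustment, before the adjusted dose passes to the next younger cohort's sentinels. Vital signs are taken for at least 4 hours after the first adjusted dose, and section 9.1.2 has hypotension stopping criteria. A reader might infer that a wrong increase would pass unchecked into younger cohorts; the DMC gate contradicts that. Within the cohort, however, only the Sponsor's review is required before the adjusted dose reaches the sentinels and later enrollees, and the stopping criteria act after events have occurred.

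4. *The size is modest.* Section 7.3.2 reports that 30 µg/kg was generally well tolerated in older children, and the refitted outputs above reach at most 20.2 µg/kg. This stands as a reason for a lower severity, though Study 111-202 did not include children this young.

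The two-fold rule might also be read as permission to increase despite over-exposure. It is a ceiling and nothing more.

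**Conclusion.** The point holds in a limited form. From a 15 µg/kg start, the expression raises dose per kg whenever the fitted pooled α is below 1, whichever trigger led to it, and the two listed rules do not prevent an increase after the high trigger. That much is algebra and needs only WT_ch < WT_ref. The sizes in the table rest on assumed weights and exponents.

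Two stronger readings are not supported. One is that the rule ignores sentinel exposure: α is re-estimated with data from this study, and a strong enough signal takes it above 1 and lowers the dose. The other is that the rule would usually raise the dose after over-exposure: that depends on the population PK model, the weights and the study sizes, none of which the protocol gives, so no frequency can be stated.

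What remains is a gap mainly within the cohort, for the sentinels at their next scheduled visit and for the subjects enrolled after them. Severity is minor to moderate, and correction is cheap.

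**What to change.** Add one rule to the list in section 9.1.1:

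> If mean sentinel AUC0-120 exceeds the 75th percentile of Study 111-202 Cohort 3, the adjusted dose/kg will not exceed the current dose/kg, and model-predicted AUC0-120 will be checked against observed sentinel AUC0-120 before the dose is applied.

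Stating the limit against the current dose, not 15 µg/kg, makes it work for later cohorts too. Qualify the targeting sentence as holding only if the fitted model describes the sentinel data. A separate reduction formula based on three sentinels is not needed.

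The cost is one rule, one qualified sentence and one clinical pharmacology check, with no new data, visits or subjects. The downside is small: if the high trigger arose by chance and α is truly below 1, the cohort stays at its current dose instead of a modestly higher one.

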9.1.2 Stopping Criteria

Individual Subject Stopping Criteria

For individual subjects treated with BMN 111, DMC will be informed if any of the following individual subject stopping criteria should occur. Temporary dosing suspension, permanent discontinuation of dosing, or dose reduction for the individual subject will be considered.

- Any treatment-emergent adverse event (AE) assessed as at least Grade 4 by the Investigator and/or Sponsor Medical Monitor
- Any treatment-emergent AE of at least Grade 3 assessed as related to study drug by the Investigator and/or Sponsor Medical Monitor
- Any two treatment-emergent Grade 2 symptomatic hypotension events within 7 days (non-urgent medical intervention indicated) or any Grade 3 hypotensive event (urgent medical intervention or hospitalization indicated) assessed by the Investigator and/or Sponsor's Medical Monitor

- Clinically significant finding or arrhythmia on electrocardiogram (ECG) that indicates abnormal cardiac function or conduction or prolongation of QTc-F > 500 msec
- Clinically significant new or worsening signs of cervicomedullary compression as determined by the Investigator and in consultation with Sponsor medical monitor and neurosurgical specialist (if needed)
- Adverse findings on clinical hip exam or hip imaging assessments that are determined to be clinically significant as determined by the Investigator and in consultation with Sponsor Medical Monitor and orthopedic specialist (if needed)

If the subject meets any stopping criterion, after Investigator consultation with the BioMarin Medical Monitor and DMC, the subject may be re-challenged at the same dose. If the subject meets stopping criteria on re-challenge or if re-challenge at same dose is not clinically indicated, other options that may be considered include:

- Re-challenge at lower dose with consideration given to upward titration to tolerated dose
- Permanent treatment discontinuation (with an option of ongoing assessment in the study)

Cohort Stopping Criteria

For each cohort, a DMC review will be conducted if any of the following cohort stopping criteria occur in subjects treated with BMN 111. Temporary dosing suspension, permanent discontinuation of dosing, or dose reduction for the cohort(s) will be considered and the impact on all other age cohorts will be assessed.

- Any treatment-emergent AE assessed as at least Grade 4 by the Investigator and/or Sponsor Medical Monitor
- Any two subjects have a treatment-emergent AE of at least Grade 3 assessed as related to study drug by the Investigator and/or Sponsor Medical Monitor
- Any two subjects have two treatment-emergent Grade 2 symptomatic hypotension events within 7 days (non-urgent medical intervention indicated) or any two subjects cohort have a Grade 3 hypotensive event (urgent medical intervention or hospitalization indicated) assessed by the Investigator and/or Sponsor's Medical Monitor
- Any two subjects have a clinically significant finding or arrhythmia on ECG that indicates abnormal cardiac function or conduction or prolongation of QTc-F > 500 msec

- Any two subjects have adverse findings on clinical hip exam or hip imaging assessments that are determined to be clinically significant as decided by principal investigator and in consultation with Sponsor medical monitor and orthopedic specialist (if needed)

9.2 Discussion of Study Design, Including Choice of Control Group

Study 111-206 is a Phase 2 randomized, double-blind, placebo-controlled clinical trial of BMN 111 in infants and younger children with a diagnosis of ACH who are age 0 to < 60 months. Identification of efficacy at this age range is congruent with mechanism of action of BMN 111, because BMN 111 is expected to act at open epiphyseal growth plates. Therefore, to have a potential therapeutic benefit for subjects with ACH, specifically for the foramen magnum and spine, treatment is expected to be required prior to growth plate closure.

In terms of the study design, a randomized double-blind placebo control will be used to mitigate the risk of selection bias and any potential bias in data collection and study conduct. Additionally, this design provides a framework for interpretation of any endpoints with a subjective component, e.g. health-related quality of life (HRQoL) and activities of daily living (ADL) questionnaires and any subjective assessment of safety.

9.3 Selection of Study Population

Subjects age 0 months to < 60 months old, with documented ACH confirmed by genetic testing, and who meet the study eligibility criteria will participate.

Additional criteria for participation in the study are provided in Sections [9.3.1](#) and [9.3.2](#).

9.3.1 Inclusion Criteria

Individuals eligible to participate in this study must meet all of the following criteria:

1. Diagnosis of ACH, confirmed by genetic testing. If subjects had previous genetic testing, subjects must have a lab report from a certified laboratory with the study specific mutation documented.
2. Age 0 to < 60 months, at study entry (Day 1)
3. Cohort 1 and 2 subjects must have at least a 6-month period of pretreatment growth assessment in Study 111-901 immediately before screening, and have one documented measurement of height/body length a minimum of 6 months prior to the screening visit for 111-206. Cohort 3 subjects must have a minimum of 3 months of observation prior to treatment. This observational period can be obtained either (1) via prior enrollment in Study 111-901 or (2) via enrollment in this Study 111-206 for a minimum of 3 months of non-treatment observation prior to commencement of treatment.

4. Parent(s) or guardian(s) (and the subjects themselves, if required by local regulations or ethics committee) are willing and able to provide written, signed informed consent after the nature of the study has been explained and prior to performance of any research-related procedure
5. Willing and able to perform all study procedures as physically possible
6. Parent(s) or caregiver(s) are willing to administer daily injections to the subjects and complete the required training

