9 INVESTIGATIONAL PLAN

9.1 Overall Study Design and Plan

This is a Phase 2 randomized, double-blind, placebo-controlled clinical trial of BMN 111 in infants and younger children with a diagnosis of ACH.

Subjects age \geq 6 months to $<$ 60 months old who have documented ACH confirmed by genetic testing; at least a 6-month period of pretreatment growth assessment in Study 111-901 immediately before study entry; and who meet the study eligibility criteria, will participate. Eligible subjects ranging from 0 months to $<$ 3 months old may enroll directly into 111-206 and have a minimum of 3 months of pretreatment observation prior to commencing treatment with investigational product, or may enroll in 111-901 for a minimum of 3 months of pretreatment growth assessment immediately before roll-over to 111-206.

Approximately 70 subjects will be enrolled at approximately 10-15 clinical centers worldwide.

The primary objectives of this study are to assess the safety and tolerability of daily SC BMN 111 administered to infants and young children with ACH, and evaluate the effect of BMN 111 on Z-scores. Subjects will be enrolled into 3 age cohorts based on age at study screening starting with the eldest population. Within Cohorts 1 and 2, subjects will be stratified by age:

- Cohort 1 – children aged \geq 24 to $<$ 60 months (n \geq 30 total: 3 sentinel subjects who receive BMN 111, and at least 27 additional subjects randomized 1:1 to treatment or placebo control), stratified by age (\geq 24 to $<$ 36 months and \geq 36 months to $<$ 60 months)
- Cohort 2 – children aged \geq 6 to $<$ 24 months (n \geq 20 total: 3 sentinel subjects who receive BMN 111, and at least 17 additional subjects randomized 1:1 to treatment or placebo control), stratified by age (\geq 6 months to $<$ 15 months and \geq 15 months to $<$ 24 months)
- Cohort 3 – children aged 0 to $<$ 6 months (n \geq 20 total: 3 sentinel subjects who receive BMN 111, and at least 17 additional subjects randomized 1:1 to treatment or placebo control). Treatment begins at \geq 3 months to $<$ 6 months after 3 months of observation.

If subjects who enroll in Cohort 3 are not able to begin treatment by $<$ 6 months of age, they will continue in the pretreatment period for another 3 months before enrolling in Cohort 2 to fulfill the pretreatment requirement for Cohort 2.

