9.3.3 Inclusion Criteria for Cohort 3 Observation Period

Individuals eligible to participate in this study must meet all of the following criteria:

1. Parent(s) or guardian(s) willing and able to provide signed informed consent after the nature of the study has been explained and prior to performance of any research-related procedure. Also, willing and able to provide written assent (if applicable) after the nature of the study has been explained and prior to performance of any research-related procedure.
2. Birth to \leq 3 months of age at study entry.
3. Have ACH, documented by genetic testing
4. Are willing and able to perform all study procedures as physically possible

After completing the observation period, subjects must fulfill the general eligibility criteria prior to receiving treatment with study drug.

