14.3 Efficacy Analysis

Efficacy analysis will be performed on the efficacy population as defined in Section 14.7.1. Efficacy endpoints include length/height AGV and length/height standard score (Z-score) at Week 52.

For a given interval [Date1, Date2], the AGV is defined as follows:

$$\text{AGV} = \frac{\text{Length/standing height at Day 2} - \text{Length/standing height at Day 1}}{\text{Interval Length (Days)}} \times 365.25$$

where the interval length in days is calculated as Date2 – Date1. AGV will be calculated for the following visits/intervals:

- Baseline: [Date of last length/height measurement in study 901 at least 6 months prior to Day 1 in study 206, Date of Day 1]
- Week 13: [Date of Day 1, Date of Week 13]
- Week 26: [Date of Day 1, Date of Week 26]
- Week 39: [Date of Day 1, Date of Week 39]
- Week 52 (12-month): [Date of Day 1, Date of Week 52]

The baseline of the AGV is established in the natural history study of Study 111-901, based on the standing height measurements in the last 6 months prior to enrollment to Study 111-206. AGV will be summarized using descriptive statistics (mean, SD, median, minimum, and maximum). Results will be summarized by treatment group and cohort.

The measurement of length/standing height will be converted to age-and sex-appropriate standard score (SDS), also referred to as Z-score, by comparison with normal reference standards (not ACH). The Z-score will be summarized similarly to growth velocity.

Comparisons between treatment groups by cohort on these variables will be carried out where appropriate. Statistical comparisons will be considered descriptive. Additional details regarding efficacy analysis will be provided in the SAP.

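### The rule moving Cohort 3 infants who age out into Cohort 2 conflicts with inclusion criterion 3, which counts only growth data collected in Study 111-901

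*Protocol*

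**What the plan says.** Infants under 3 months have two ways in. Section 9.1 says they "may enroll directly into 111-206 and have a minimum of 3 months of pretreatment observation prior to commencing treatment", or they may first be followed in Study 111-901. For those who miss the Cohort 3 age limit, the same section says "they will continue in the pretreatment period for another 3 months before enrolling in Cohort 2 to fulfill the pretreatment requirement for Cohort 2". The synopsis has the same rule.

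Inclusion criterion 3 in 9.3.1, also repeated in the synopsis, reads: "Cohort 1 and 2 subjects must have at least a 6-month period of pretreatment growth assessment in Study 111-901 immediately before screening". It adds that the child must "have one documented measurement of height/body length a minimum of 6 months prior to the screening visit for 111-206". The route "via enrollment in this Study 111-206 for a minimum of 3 months of non-treatment observation prior to commencement of treatment" is offered only as a source for the Cohort 3 observation period. The opening eligibility sentence of Section 9.1, for children of 6 months and older, likewise names Study 111-901 as the source.

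Section 9.3.3 closes with: "After completing the observation period, subjects must fulfill the general eligibility criteria prior to receiving treatment with study drug". Section 9.3.4 ends the same way.

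Section 14.3 defines the baseline interval for annualized growth velocity (AGV) as: "Date of last length/height measurement in study 901 at least 6 months prior to Day 1 in study 206, Date of Day 1".

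**The concern.** Section 9.1 tells sites to move an aged-out infant to Cohort 2 and says the extra time satisfies the requirement there. Criterion 3 then refuses that time if it was spent in 111-206. Eligibility is fixed by the protocol, so an analysis plan cannot settle the matter later.

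A site would have to turn away a child after about 6 months of observation, send the child for a fresh period in 111-901, or enrol the child as an eligibility deviation. Sites could resolve it differently. Cohort 2 is small (at least 20 children, of whom at least 17 are randomised), so even a few inconsistent decisions would be visible.

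The baseline AGV definition also depends on a Study 901 measurement, and change from baseline in AGV is a secondary endpoint.

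**Working it through.** The protocol states no power, error-rate or sample-size figure that bears on this point, so there is nothing to reproduce. The check counts pretreatment months by source study and compares them with the rules.

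**Criterion 3 for an aged-out infant.** Inputs: 3 months of minimum observation plus 3 added months (Section 9.1); 6 months required in 111-901 (9.3.1).

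| Route | Total months | Months in 111-901 | Required in 111-901 | Criterion 3 |
|---|---|---|---|---|
| All in 111-206 | 3 + 3 = 6 | 0 | 6 | fails |
| 3 in 111-901, then 3 in 111-206 | 3 + 3 = 6 | 3 | 6 | fails |
| All in 111-901 | 3 + 3 = 6 | 6 | 6 | met |

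The total is always right; only the named source study causes the failure. Sections 9.3.3 and 9.3.4 apply the general criteria to every child leaving observation and carve out nothing for age-outs.

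**Can ageing out happen?** Treatment in Cohort 3 must start before 6 months of age, after at least 3 months of observation. For an infant who enters at age e months, the time left to start is 6 − (e + 3) = 3 − e months. That is 3 months for entry at birth and 0 for entry at 3 months. Section 9.3.3 admits infants up to and including 3 months, so an infant entering at that limit reaches 6 months of age as the minimum observation ends and is already outside the cohort. Section 9.1 writes a rule for this case, so it was foreseen.

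**Baseline AGV interval (14.3).** The interval must start at a Study 901 measurement at least 6 months before Day 1.

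- Child observed only in 111-206: no Study 901 measurement exists, so the interval is undefined.
- Any child treated in Cohort 3, by either route: age at Day 1 is at least 3 and less than 6 months. The latest allowed starting age is therefore between 3 − 6 = −3 months and just under 6 − 6 = 0, which is before birth. The interval cannot exist.
- Aged-out child who began in 111-901: defined, provided the first 111-901 measurement is at least 6 months before Day 1.

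Section 7.3.1 says that 111-901 collects at least 3 months of data for Cohort 3. That confirms that a 6-month baseline interval does not fit that cohort.

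**Are the measurements there?** Table 9.1.2 schedules anthropometry at Month 0 and at 3 months of observation. Table 9.1.1 schedules it at screening and on Day 1 of treatment. An aged-out child therefore has a length at both ends of a 6-month interval. The data exist; the wording excludes them.

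**The case against.** The best defence is that the intent is plain. Section 9.1 is the specific rule for these infants and states its purpose, and the durations add up. On that view criterion 3 simply carries a source-study label that was never updated. That is fair as an account of how the conflict arose, and it makes the repair uncontroversial. It does not make the child eligible: 9.3.3 and 9.3.4 refer back to the general criteria, and a monitor would check against those.

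Several stronger readings are tempting, and the documents do not support them.

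- A reader might infer that these children are permanently shut out. They are not. Study 111-901 is ongoing, Cohort 2 runs to under 24 months, and nothing shown bars a fresh 6 months there. That is a costly delay, and it contradicts the 3 added months in Section 9.1, but it is a way in.
- A reader might attach a number, for example 10–30% of 20 infants, or 2–6 children. The protocol gives no age-out rate and no split between routes. The 20 (3 sentinels plus at least 17 randomised) is also the wrong denominator, because it counts children in Cohort 3, a group that age-outs leave.
- A reader might expect frequent age-outs because of the wait for Cohort 2 sentinels and the data monitoring committee. That wait precedes the opening of Cohort 3. It uses up an infant's window only if observation starts earlier, which the protocol does not say.
- A reader might see a missing visit, since Table 9.1.2 stops at 3 months. The Cohort 2 screening and Day 1 anthropometry in Table 9.1.1 serve the purpose.
- A reader might treat the AGV gap as a result of ageing out. It is wider: it covers every child treated in Cohort 3, so merely allowing 111-206 measurements in the 6-month interval would not close it.

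**Conclusion.** The contradiction stands in the current text. An infant observed partly or wholly within 111-206 fails criterion 3 when the age-out rule in Section 9.1 is followed. That child then needs a new 6 months in 111-901 or enters as an eligibility deviation. This rests on the literal wording of 9.3.1, with no exemption in 9.3.3 or 9.3.4. How many children are affected cannot be computed from the protocol.

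Separately, the 14.3 baseline AGV interval is undefined for children observed only in 111-206 and for all children treated in Cohort 3. This affects a secondary endpoint whose comparisons 14.3 calls descriptive. The primary endpoint, change in length/height Z-score, does not use that interval. The point should be fixed, but it does not threaten the main analysis.

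**What to change.** 1. Amend criterion 3 in 9.3.1 and the synopsis so that the 6 months for Cohort 2 may come from Study 111-901, the 111-206 observation period, or both. Bring the opening eligibility sentence of Section 9.1 and its synopsis counterpart into line.
2. Amend the baseline AGV interval in 14.3, and the sentence below it on where the baseline is established, to accept measurements from the 111-206 observation period. For Cohort 3, define an interval that matches its 3-month minimum observation.

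The cost is a few clauses in 9.3.1, 9.1, the synopsis and 14.3. No subjects or visits are added, and no dose or treatment rule changes.
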